□ 5) Research involving materials (data, documents, records, or specimens) that have been collected or will be collected solely for nonresearch purposes (such as medical treatment or diagnosis). (Note: Some research in this category may be exempt from the HHS regulations for the protection of human subjects. [45 CFR 46.101\(b\)\(4\)](#). This listing refers only to research that is not exempt.)

□ 6) Collection of data from voice, video, digital, or image recordings made for research purposes.

□ 7) Research on individual or group characteristics or behavior (including, but not limited to, research on perception, cognition, motivation, identity, language, communication, cultural beliefs or practices, and social behavior) or research employing survey, interview, oral history, focus group, program evaluation, human factors evaluation, or quality assurance methodologies. (Note: Some research in this category may be exempt from the HHS regulations for the protection of human subjects [45 CFR 46.101\(b\)\(2\) and \(b\)\(3\)](#). This listing refers only to research that is not exempt.)

PROJECT INFORMATION

Title of Project: (If applicable, use the exact title listed in the grant/contract application). 

IRB Share / Novel Actions of Metformin to Augment
Resistance Training Adaptation in Older Adults

Short Title Description

Note: "Short Title" should consist of a couple key words to easily identify your study - these key words (rather than the whole title) will be displayed on the Dashboard in the listing for your study.

MASTERS

Anticipated Ending Date of Research Project: 12/31/2019

Number of human subjects  40

Study is/will be open to new subject enrollment (or data/specimen collection):  Yes No

PI CONTACT INFORMATION

The Principal Investigator's (PI) contact information is filled in automatically based on who was logged in when the application was created (with LinkBlue ID). If research is being submitted to or supported by an extramural funding agency such as NIH, a private foundation or a pharmaceutical/manufacturing company, the PI listed on the grant application or the drug protocol must be the same person listed below.

If you are not the Principal Investigator, do NOT add yourself as study personnel. You may change the PI contact information on an application that is in Researcher edit mode by:

- clicking the "Change Principal Investigator" link below;
- searching for the PI's name using the search feature;

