- (Risk Level 3) Greater than minimal risk, no prospect of direct benefit to individual subjects, but likely to yield generalizable knowledge about the subject's disorder or condition.
- (Risk Level 4) Research not otherwise approvable which presents an opportunity to understand, prevent, or alleviate a serious problem affecting the health or welfare of subjects.

*"Minimal risk" means that the probability and magnitude of harm or discomfort anticipated in the research are not greater in and of themselves from those ordinarily encountered in daily life or during the performance of routine physical or psychological examination or tests [[45 CFR 46.102\(i\)](#)]

Download UK's guidance document on assessing the research risk for additional information on risk [[PDF](#)] 

SUBJECT DEMOGRAPHICS

Age level of human subjects: (i.e., 6 mths.; 2yrs., etc..) to

Indicate the targeted/planned enrollment of the following members of minority groups and their subpopulations
(Please note: The IRB will expect this information to be reported at Continuation Review time):

Enter Numbers Only!		
Ethnic Origin	#Male	#Female
American Indian/Alaskan Native:		
Asian:		
Black African American:		
Hispanic/Latino:		
Native Hawaiian/Pacific Islander:		
White/Caucasian:		
Other or Unknown:		

If unknown, please explain why:

Indicate the categories of subjects and controls to be included in the study. Depending on the subject category applicable to your research you may be required to complete additional forms. [Note, if the study does not involve direct intervention or direct interaction with subjects, (e.g., record-review research, outcomes registries), do not check mark populations which the research does not specifically target. For instance, a large record review of a diverse population may incidentally include a prisoner or an international citizen, but, if the focus or intent of the study has nothing to do with that status, you do not need to check those category(ies).]

Check All That Apply (at least one item must be selected)

ADDITIONAL INFORMATION:	

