We have assembled a dual-site team (UK and UAB) of established investigators with complementary skills and a wealth of pertinent experience to conduct a randomized, double-blind, placebo-controlled trial that is centered on a novel, alternative use of metformin. This will be the first known metformin repurposing trial to test the potential impact of combined exercise-drug therapy on muscle mass and function, and it will be conducted in an aging cohort most in need of a treatment that maximizes muscle regrowth and strength gain. The two site design ensures that recruitment goals will be met and data analyzed within the duration of the granting period. Because a more diverse population will be studied than at either site alone, results obtained will be more generalizable. Subjects will also be stratified and randomized by site and by functional status. Data Collection Schedule (Table 1). This protocol involves ~17 wk of participation. Subjects will complete assessments at the CTSA-sponsored clinical services cores at each site. Pre-treatment. Following physical exam and detailed screening, baseline tests will include: (i) short physical performance battery (SPPB), functional tests of balance, gait speed, ; (ii) a fasting blood draw to assess liver and kidney function, glucose, insulin, and electrolytes (repeated at midpoint of the PRT period to monitor liver and kidney function for safety) Vit D and other blood tests that may be related to muscle function or insulin resistance could also be assessed ; cell isolation; (iii) an oral glucose tolerance test (OGTT); (iv) whole body dual-energy x-ray absorptiometry (DXA) scan along with circumferences; (v) vastus lateralis muscle biopsy and mid-thigh CT; (vi) 4 day diet record and physical activity monitoring; and (vii) self reported quality of life involving several questionnaires. Subjects will also be introduced to the strength and power testing. Subjects will then be randomized and sent home with instructions and a 2 wk supply of metformin or placebo (in double-blind fashion). Week 2. After 2 wk of metformin/placebo, fasting blood, and muscle biopsy will be repeated. Baseline strength and power tests will be performed and pills counted for compliance. Strength and power testing at this time will be primarily used as a second familiarization and practice testing session, to account for the well-known motor learning effects that can dramatically influence performance during maximal testing of naïve subjects. Resistance training will then be introduced and progressed over a 2 wk period. Week 4. After the first 2 wk of resistance training familiarization and ramping, strength and power testing will be repeated and considered true baseline muscle performance, followed by 12 wk of PRT at full volume and intensity. Week 9. Strength and power testing will be performed halfway through the PRT program along with a safety check blood draw. Week 16. All dependent variables will be re-assessed within 5 days post-training; strength, power and SPPB on the final day of training; muscle biopsy, OGTT, blood draw, CT, circumferences, questionnaires, and DXA on subsequent visits. Long Term Follow Up. We plan to contact those individuals that may be interested in returning to perform certain assessments including strength and power, quality of life, as well as physical function and activity monitoring at 26 and 52 weeks after initial evaluation. During the 14 wk of PRT (2 wk of familiarization and ramping; 12 wk of full volume PRT), participants will report 3 times per wk to exercise and to obtain the necessary number of capsules. The exercise physiologists supervising training and compliance and technicians/nurses performing scans/tests will be blinded to drug treatment and will perform all analyses using methods standardized between sites. Retention. We expect voluntary attrition rate to be approximately 20%, slightly higher than in our prior resistance training studies in deconditioned older adults (15%). Compliance. Ideally all subjects would attend 100% of scheduled resistance exercise sessions and will consume all prescribed doses of metformin or placebo, but we have sufficient experience with these types of intensive trials to recognize that this ideal scenario is not realistic. For this project, the goal will be 3 d/wk resistance training, but subjects who complete at least 5 of 6 sessions every two weeks will be considered in good standing. Subjects will be given pre-configured dosages with instructions to return unused containers; visiting the facility 3 times per week for exercise training will facilitate compliance. In cases where a pattern of noncompliance develops, the study coordinators will prompt participants with evening phone calls.

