One hundred males and females (n=60 at UAB completed in years 1-4; n=40 at UK in the first 2½ years of the award) =65 years of age with a short physical performance battery (SPPB) score of >3 (score range 0-12) will be studied. These represent non-disabled and mobile individuals who are able to participate in the functional testing and resistance exercise. The recruitment distribution between sites is based on past recruitment/retention experience with PRT trials, and it will enable UK team members to focus on tissue analyses in years 3-5. Given the anticipated attrition rate of 20%, we will recruit 120 participants (72 UAB and 48 UK) to achieve a final sample size of 100 (50 metformin, 50 placebo), which will allow sufficient power for "as observed" comparisons. Approximately equal numbers of men and women of all races and ethnicities will be recruited from the Centers on Aging, through the CTSA Volunteer Opportunities Websites at both institutions, and through general advertisements. Human subjects recruited into this study will have no history of resistance training (>2x per week consistently) within the past year, and no contraindications to being in the study (see inclusion/exclusion criteria below). Inclusion criteria • =65 years of age. • Independently mobile with a SPPB score 3-12. • Access to transportation. • Capable of providing informed consent (cognitively intact). Exclusion criteria • Obesity (BMI>30) • Serum creatinine >1.4 because of risk of lactic acidosis with metformin. • History of regular resistance training within the past year. • History (or ECG evidence) of previous myocardial infarction, history of congestive heart failure. • Current angina pectoris or symptoms of myocardial ischemia or congestive heart failure. • Chronic aspirin or NSAID use (unless it can be safely stopped prior to the biopsies), and any other use of an anticoagulant (e.g., Coumadin) or history of bleeding. • History of alcoholism or liver disease. • History of hypo- or hyper-coagulation disorders including subjects taking Coumadin. • Any end-stage disease and/or a life expectancy less than one year. • Neurological, musculoskeletal, or other disorder that would preclude them from completing resistance training and all performance tests. • Uncontrolled hypertension. • Diabetes mellitus as demonstrated with- HgbA1C>6.5, or fasting glu>126 mg/dl. • Any other medical condition that would interfere with testing or increase one's risk of complications during exercise, as judged by the study physicians. • Any other condition or events considered exclusionary by the PI and/or physician, such as non-compliance. • Lidocaine allergy (1% lidocaine is the local anesthetic used during the muscle biopsy procedure). Estrogen/progesterone hormone (HRT) replacement therapy will not be an inclusion or exclusion criterion as this does not affect gains in muscle strength or lean mass during resistance training.

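### The UK application states two UK enrolment numbers: 40 in the form field and demographic table, 48 in the recruitment text, where 40 is the post-attrition target

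*Combined protocol and SAP*

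**What the plan says.** Three places in the UK application bear on the UK number.

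- **Project Information.** The entry reads "Number of human subjects 40". The field is not further defined.
- **Subject Demographics.** The table is introduced with "Indicate the targeted/planned enrollment of the following members of minority groups and their subpopulations". Its filled cells are 1, 2 and 16 for men and 1, 3 and 17 for women, with zeros elsewhere and the row for other or unknown left blank. The form adds that this information is to be reported at continuation review.
- **Study Population.** The number to be studied is 100, split as "n=60 at UAB completed in years 1-4; n=40 at UK in the first 2½ years of the award". Citing 20% attrition, the same paragraph then says "we will recruit 120 participants (72 UAB and 48 UK) to achieve a final sample size of 100", with 50 in each arm.

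The retention text under Study Design also puts voluntary attrition at about 20%, and gives 15% for the team's earlier resistance-training studies.

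**The concern.** In Study Population, 40 and 48 are different quantities: 40 is what UK contributes to the final sample, and 48 is what it recruits to get there. The form field and the table show only 40, and the table is explicitly labelled as planned enrolment. The completer target appears to have been carried into places that call for the number enrolled.

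The site's recruitment target depends on which figure staff use. Someone working from the form would stop 8 people short of what Study Population requires, and the trial would then expect fewer completers than its own recruitment plan delivers. The count given to the IRB also matters because the application rates the study as greater than minimal risk (Data and Safety Monitoring) and plans three muscle biopsies per participant. It should give a single figure for how many people UK will enrol.

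**Working it through.** **Inputs.** UK form entry: 40 (Project Information). Table cells: Subject Demographics. Final sample 60 + 40 = 100 and recruitment 72 + 48 = 120: Study Population. Attrition 20%: Study Population and Study Design. Alternative rate 15%, from earlier studies: Study Design.

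**Step 1: table total.** Men 0 + 1 + 2 + 0 + 0 + 16 = 19. Women 0 + 1 + 3 + 0 + 0 + 17 = 21. Total 19 + 21 = 40, equal to the form entry.

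**Step 2: reproduce the plan's recruitment figures.** Multiplying the final sample by (1 + 0.20):

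- UK: 40 × 1.20 = 48
- UAB: 60 × 1.20 = 72
- Total: 100 × 1.20 = 120

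All three match Study Population exactly, so 40 is the figure before the attrition allowance and 48 the figure after it. The two-site totals are 100 and 120, so the form's 40 can correspond only to UK.

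**Step 3: expected completers**, as enrolled × (1 − attrition):

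| | UK enrols 48 | UK enrols 40 | Difference |
|---|---|---|---|
| UK, 20% attrition | 48 × 0.80 = 38.4 | 40 × 0.80 = 32 | 6.4 |
| UAB, 20% attrition | 72 × 0.80 = 57.6 | 57.6 | 0 |
| Trial, 20% attrition | 120 × 0.80 = 96 | 112 × 0.80 = 89.6 | 6.4 |
| UK, 15% attrition | 48 × 0.85 = 40.8 | 40 × 0.85 = 34 | 6.8 |
| Trial, 15% attrition | 120 × 0.85 = 102 | 112 × 0.85 = 95.2 | 6.8 |

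Per arm under 1:1 allocation, 6.4 / 2 = 3.2.

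**Step 4: separate the two sources of shortfall.** At 20% attrition with UK at 40, the gap to the stated final sample is 100 − 89.6 = 10.4. Of this, 96 − 89.6 = 6.4 comes from the mismatch between 40 and 48. The other 100 − 96 = 4 arises because the plan multiplied by 1.20 instead of dividing by 0.80; division gives 100 / 0.80 = 125 overall and 40 / 0.80 = 50 at UK. Correcting that formula would leave both form entries at 40, so the two problems are distinct.

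**The case against.** The strongest reply is that this is a labelling slip in one site's form. The figure of 48 stands in the same application, so the IRB was given it, and the field under Project Information says only "Number of human subjects", which could be read as completers. That reading does not dispose of the point, because the table carries the same total under a planned-enrolment label. The table's other-or-unknown row is blank and some form values were lost in extraction, but agreement between its sum and the form entry makes a missing count unlikely.

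The rest of the reply stands, and it rules out several stronger inferences.

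- **That 40 is a ceiling, so enrolling 48 would be non-compliant or would compromise those participants' data.** The text calls 40 neither a maximum nor an approved limit, and states no rule on exceeding it. The approval letter, a continuing-review file and a study-design attachment are listed but not reproduced.
- **That UK will consent more than 48 people.** Research Procedures places consent before the examination and laboratory screens and makes final enrolment depend on passing them. Study Population does not say whether the 48 are counted before or after those screens.
- **That the mismatch costs about 10 completers.** Step 4 shows that it accounts for 6.4.
- **That power falls by a known amount.** The text supplied gives no effect size, standard deviation or power figure, so this cannot be computed.

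Current UK accrual is not shown, so it is also unknown whether the site still has to choose between the two numbers.

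**Conclusion.** The contradiction is real. The UK application states 40 in two places and 48 in a third as the number to be taken in at UK, and does not reconcile them. The form has used the post-attrition target as planned enrolment.

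If UK worked to 40, the expected loss is 6.4 completers at 20% attrition, or 6.8 at 15%: a little over 3 per arm either way. UK would end with about 32 (34 at 15%) and the trial with about 90 (95 at 15%). These sizes assume that UAB recruits its 72 and that the same attrition rate applies at both sites.

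The finding concerns inconsistent sample-size figures. It does not show over-enrolment or misconduct, and it leaves the design and analysis untouched.

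**What to change.** 1. Under Project Information and Subject Demographics, enter the number UK is to enrol: 48 as Study Population now states, or its replacement if the attrition allowance is corrected (50 on division by 0.80). Redistribute the table to the same total.
2. Label 40 wherever it appears as the UK completer target.
3. State whether the enrolment number includes people who consent and then fail screening.
4. If UK intends to enrol only 40, leave the form as it is and restate the UK and total recruitment and the final sample in Study Population (at 20% attrition with 72 at UAB, about 32 at UK and about 90 overall).

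The cost is a modification to one site's form, or to one paragraph under the fourth option. No procedure changes, and entering 48 adds nobody beyond those Study Population already plans to recruit. Adopting 50 would add two at UK, but that decision belongs to the separate attrition-allowance issue.

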Respondents that appear to qualify based on an initial screen (phone or web; see submitted forms), will come in for a face-to-face interview that will begin with the informed consent process. Each volunteer must pass a careful history which will include additional questionnaires such as the PAR-Q and other health screens, a physical exam, electrocardiogram (ECG). These will be performed in the CCTS under supervision of the study physician, PA, CCTS nursing personnel, and an exercise physiologist. Respondents will also perform the Short Physical Performance Battery (SPPB) and complete a fasting blood draw where some of the blood can also be prepared for monocyte isolations. Final enrollment decisions will be contingent upon successful completion of all screens, including passing the physical exam and acceptable laboratory results (creatinine, glucose, liver enzymes, TSH, CBC with platelets, HgbA1C). Short Form 36 (SF-36). The SF-36 survey is a multi-item scale designed to assess health related quality of life among eight domains. These include physical functioning, role limitations due to physical health problems, bodily pain, general health perceptions, vitality (energy and fatigue), social functioning, role limitations due to emotional problems, and mental health. It has demonstrated excellent reliability and validity in older adults and across various populations. Physical Activity Measures. The Physical Activity Survey for the Elderly (PASE) as well as physical activity monitors will be used in this study. The PASE is a self report or interview based measure designed to capture and assess occupational, household, and leisure activities typically performed by older adults including those of lighter intensity. Time spent participating in each activity area is multiplied by a weighted value that reflects the amount of energy expended by an older person engaged in that activity. These weighted values are then summed to yield a composite PASE score. This questionnaire has been found to be both reliable and valid among community dwelling and physically disabled older adults. Our physical activity monitor will be worn on the wrist and will have accelerometry, HR monitoring, and sleep pattern capabilities. PROMIS modules. PROMIS uses modern measurement theory to assess patient-reported health status for physical, mental, and social well-being to reliably and validly measure patient-reported outcomes (PROs) for clinical research and practice. PROMIS instruments are generated from item banks. PROMIS' measures can be used as primary or secondary endpoints in clinical studies of the effectiveness of treatment. SPPB functional testing. The three timed standing balance tests (side-by-side, semi-tandem and tandem), 4-meter gait speed test performed twice, and timed repeated chair sit to stand (5 times) will be performed 1. Performance for each set of tasks is scored (0-4), with a summary score of 0-12. Muscle strength and power testing. Voluntary,

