
dynamic strength will be evaluated by testing a one repetition max (1-RM), defined as the maximal load that a subject can lift one time with proper form through a full range of motion, via our well-established methods 2-4 that have been standardized across sites. After warm-up, single repetition trials (separated by 1-2 min rest) are performed with increasing resistance until two failed attempts at a given load. The last successfully lifted load with good form will be recorded as the 1-RM. We will also evaluate maximum voluntary isometric knee extension strength using our established methods on a Biodex 4 dynamometer 5, available at both sites. Knee extension concentric power will also be determined using the Biodex set on isotonic mode to allow for variable velocities with a constant external load equal to 40% of maximum voluntary isometric strength. OGTT. A standard 2 hr OGTT will be performed after a 8-12 hr fast using 75 g glucose. Blood will be drawn before and 30, 60, 90 and 120 min after ingestion for measurement of glucose and insulin, and the Matsuda index, which correlates well with the euglycemic clamp 6 will be used to calculate insulin sensitivity. DXA. Body composition (whole body, regional fat and lean mass) and bone mineral density will be determined using a Lunar Prodigy (UAB) and an IDXA (UK) and standardized methods for regional partitioning. Data quality will be assured by phantom calibrations. Each participant will receive a DXA scan performed at the CCTS in the University of Kentucky Medical Center by study personnel trained in this procedure. The subjects will be instructed to remove all objects such as jewelry or eyeglasses and will wear a hospital gown, or a light weight shirt and shorts (containing no metal) during the scanning procedure. If a woman of childbearing potential is to be scanned, a pregnancy test will be conducted prior to the scan. The scan takes approximately 8-10 minutes to complete. All scans will be analyzed by a trained and certified investigator using the GE Lunar software version 10.0. DXA bone mineral content (BMC; kg), DXA bone mineral density (BMD; g/cm²), DXA fat-free mass (FFM; kg), DXA mineral-free lean mass (MFL; kg), DXA fat mass (Fat; kg), and DXA percent fat (%Fat) will be assessed. Anthropometry (Circumferences). Circumferences will be taken at various places on the upper body including the waist, abdomen, and hip etc. All measures will be taken by rotating through measurement sites and taking duplicate measures at each site if measures are not within proper ranges. All measures will be on the right side of the body to stay in accordance with ACSM guidelines. Computed Tomography (CT). Single Slice CT images (Siemens Definition) will be used to quantify skeletal muscle and fat area of the right and left thighs of each subject using 100mA with a scanning time of 3 s and a 512 X 512 matrix. With the subject supine, one 5-10 mm thick cross-section scan of both legs will be taken corresponding to the midpoint between the inguinal crease and the proximal border of the patella (the midthigh). Tissue area quantification will be determined using corresponding attenuation values of =200HU; -190 to -30 HU; and 0-100 HU for bone, adipose tissue, and skeletal muscle respectively using available software (NIH ImageJ; <http://rsbweb.nih.gov/ij/>). Total thigh fat will be further subdivided into two compartments including the fat above the fascia latae (subcutaneous thigh fat) and below the fascia latae (deep thigh fat). In addition, the skeletal muscle will be subdivided into areas of low attenuation (0-34 HU) representing fat rich muscle, and high attenuation values (35-100 HU) representing muscle with normal fat content. Images obtained as dicom files from UK Radiology will also be sent to the University of Arkansas Medical School and/or Central Arkansas Veterans Healthcare Administration for evaluation with another medical image analysis platform called sliceomatic. All images will be deidentified so that each subject will remain anonymous and only coded with their study identification number. Muscle biopsies. Three muscle biopsies (approximately 250 mg each) will be obtained from the vastus lateralis after local anesthetic (1% lidocaine) using a 5 mm Bergstrom needle with suction. As described above, there will be a baseline muscle biopsy, another at 2 weeks of drug/placebo treatment, and the final biopsy at 16 weeks. This procedure is routinely performed at both sites using the same processing method, with subjects returning for multiple biopsies. Muscle tissue will be divided as follows: 100 mg will be processed for myoblast isolation (Aim 3); ~100 mg will be snap frozen (~30 mg aliquots) in liquid nitrogen for RNA and protein isolation (Aim 2); and ~50 mg will be mounted in tragacanth gum and frozen in liquid nitrogen-cooled isopentane for detailed immunohistochemical (IHC) analyses (Aim 2), including myofiber CSA (Aim 1). Dietary monitoring. Participants will be asked to maintain their normal dietary intake throughout the study period. Energy intake and macronutrient composition will be assessed by 4 day diet records on each of the testing visits (Table 1). The nutrient content will be determined by those qualified to use the Nutrition Data System for Research, which utilizes the multiple-pass method to help improve the validity of dietary data 7. Randomization to Drug or Placebo. After informed consent and all tests to establish eligibility, participants will be randomized to receive either placebo or metformin treatment for 2 wk, followed by a 14 wk PRT program, with continued drug or placebo. Every effort will be made to conduct the randomization so that the metformin and placebo groups are equivalent. Since recruitment at UAB is expected to be more than at UK, participants will be stratified by site prior to randomization. Additionally, SPPB score will also be used for stratification. Randomization, stratified by site (UAB vs. UK) and by functional status (SPPB 3-8 vs. 9-12), will be implemented in permuted blocks of 4 using SAS v9.2 PROC PLAN to ensure adequate distribution of all groups across the collection period. In the event that other variables prove to be different between the two groups and have an impact on the outcome, covariate-adjusted analyses will be utilized as described below. Subjects randomized to metformin (850 mg each capsule) will take increasing doses as follows: 1 capsule (850 mg) per day for 7 days, 2 capsules per day (1700 mg) for 7 days, the latter being the target clinical dose, continued throughout the 14 wk of PRT. In some subjects, the dose progression may be slower and may not reach 1700 mg/day due to GI side effects. The placebo capsules will look identical to the metformin capsules, but will contain inert substances, and the escalating dose schedule will be the same. The metformin and placebo tablets will be obtained commercially through different facilities. The placebo tablets will be obtained from the VA Cooperative Studies Program Clinical Research Pharmacy Coordinating Center, which is in New Mexico (working through their non-profit foundation, the Biomedical Research Institute of New Mexico). This program is registered with the FDA as a manufacturing, packaging and distribution facility and serves the needs of VA studies, as well as NIH funded and some industry studies. We will contract with this facility to supply us with metformin placebos. There are many different manufacturers of metformin, and the VA facility in New Mexico will provide us with a tablet which will be identical to metformin 850 mg tablets that are manufactured by Amneal Pharmaceuticals, which is an established generic drug maker. Therefore, we will obtain placebo tablets from the New Mexico VA facility, and we will purchase generic (Amneal) 850 mg metformin tablets through our investigational pharmacy. Progressive resistance exercise training (PRT). The 14 weeks of PRT (42 sessions ± 3-5 sessions) will be supervised by trained personnel (exercise physiologists, or senior level physical therapy or athletic training graduate students under the supervision of an exercise physiologist). Each site has a certified, lead exercise physiologist with several years of experience, responsible for managing the day-to-day activities and supervising all trainers. Subjects will be instructed on proper techniques and continuously monitored. Following warm-up, PRT will consist of 8 constant load movements to train all major muscle groups (leg press, knee extension, one legged squat, calf press, chest press, lat pull down, biceps curl, and triceps pressdown). All resistance exercises will be performed bilaterally, progressing to reach full volume and intensity for each exercise by the end of wk 2. We will implement a variable intensity prescription: "high-low-high" 3 d/wk program. On Mondays and Fridays, intensity will be high – subjects will complete 3 sets of 8-12 repetitions at 70-75% 1-repetition maximum (1-RM) with 60-90s between sets. Progression will be incorporated continuously by incrementing the resistance load when 12

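### The SPPB summary stops at 12 and volunteers may enter at 12, so an arm difference in function at Week 16 is pulled toward zero; gait speed and chair-stand time should be added as continuous outcomes.

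*Combined protocol and SAP*

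**What the plan says.** The Study Design section gives function as a target of the trial, which is to "test the potential impact of combined exercise-drug therapy on muscle mass and function". The SPPB is a baseline test, listed as "short physical performance battery (SPPB), functional tests of balance, gait speed". It returns among the dependent variables re-assessed at Week 16, with "strength, power and SPPB on the final day of training".

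Under Research Procedures, the SPPB paragraph describes timed balance tests, and then "4-meter gait speed test performed twice, and timed repeated chair sit to stand (5 times) will be performed". Its scoring sentence is: "Performance for each set of tasks is scored (0-4), with a summary score of 0-12". No other scoring or functional endpoint derived from these tasks is stated.

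In Study Population, the inclusion criterion is "Independently mobile with a SPPB score 3-12". Of the intended participants that section says: "These represent non-disabled and mobile individuals who are able to participate in the functional testing and resistance exercise". Obesity, diabetes, previous myocardial infarction, heart failure and disorders that preclude training are exclusions. Randomization is stratified at SPPB 3-8 versus 9-12, so the upper stratum includes the scale maximum. The Benefit vs. Risk section expects all participants to benefit from the training.

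Aim 1 (Objectives) names muscle size, strength and insulin sensitivity. It does not name the SPPB.

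**The concern.** A participant who enters at 12 cannot gain on the summary, and one who enters at 11 can gain at most one point. The eligibility criteria favor high scorers, and training moves both arms upward. Part of any real advantage of metformin would therefore fall above the top of the scale and go unrecorded. On the summary, the arm difference is biased toward zero, most of all in the 9-12 stratum.

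At stake is how a null result would be read. Absence of a functional benefit and absence of room on the scale would look the same. Yet two of the tasks behind the score yield times that do not stop at a fixed top category, and these are already collected.

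**Working it through.** **1. Inputs.** From Study Population: 120 recruited and 20% attrition expected. 120 × (1 − 0.20) = 96, or 48 per arm. (The stated target is 50 per arm; the difference is immaterial here.) From the SPPB paragraph and inclusion criteria: integer score, maximum 12, entry 3-12.

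The text supplied gives no SPPB standard deviation, pre/post correlation, expected effect or share at 12, and no SPPB power figure to reproduce. These are therefore assumptions: SD 2 points, correlation 0.7, training gain 0.6 points in both arms (0.3 SD), drug effect 0.8 points (0.4 SD), two-sided α 0.05.

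**2. Uncapped reference.** For analysis of covariance on an unbounded version of the composite:

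SE = SD × √(1 − ρ²) × √(2/n) = 2 × √0.51 × √(2/48) = 0.2915

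0.80 / 0.2915 = 2.744; power = Φ(2.744 − 1.960) = 78%

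Simulation gives about 77%.

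**3. Capped score.** The same latent values are rounded and limited to 3-12 at both visits. Scores may fall as well as rise. The latent mean is set so that the chosen share of entrants scores 12.

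| Share at 12 at entry | Observed effect (points) | Power |
|---|---|---|
| uncapped | 0.80 | about 77% |
| 10% | 0.68 | about 71% |
| 20% | 0.58 | about 66% |
| 40% | 0.40 | about 54% |

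With 3,000 runs, the Monte Carlo standard error near 54% is √(0.54 × 0.46 / 3000) = 0.9 percentage points. Repeat runs at the 40% setting gave 52% to 55%.

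**4. How far up the range is plausible.** At 60% or 70% at 12, power in this model falls to about 39-41% or 31%. The latent mean would then be about 12.0 or 12.5, and the share scoring 8 or less is Φ((8.5 − 12.0)/2) ≈ 4% or Φ((8.5 − 12.5)/2) ≈ 2%. That is about 5 or 3 of 120 recruits in the 3-8 stratum. A plan that stratifies on 3-8 presumably expects more, so these rows are left out of the conclusion.

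**5. Different assumptions, same direction.** With 50 per arm, latent SD 2, measurement SD 1, placebo gain 0.5 and drug effect 0.6 points, power is about 86% uncapped. It is 74%, 69% and 57% on the capped score with 12%, 24% and 41% at 12.

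**6. What the reference does not show.** The 77% belongs to a hypothetical uncapped composite. A single timed task has its own effect and noise. Using power = Φ(effect/SE − z) in SD units, with 48 per arm:

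- effect 0.3, ρ 0.7: SE = √0.51 × √(2/48) = 0.1458; Φ(2.058 − 1.960) = 54%
- effect 0.4, ρ 0.5: SE = √0.75 × √(2/48) = 0.1768; Φ(2.263 − 1.960) = 62%
- effect 0.4, ρ 0.7, α 0.025 for two outcomes: Φ(2.744 − 2.241) = 69%

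Each of these is within the range that the capped composite covers in step 3.

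**The case against.** Four objections have weight.

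- **Nothing says that only the summary will be analyzed.** The scoring sentence describes the instrument. The baseline list in Study Design names gait speed beside the SPPB and then breaks off. The randomization paragraph points ahead to analyses that are not in the text supplied, and Table 1 and the attached design form are not reproduced. A plan for the timed tasks may exist there. This stands, and it makes the point conditional: on the text available, the times have no stated analysis.
- **The SPPB is not an Aim 1 outcome.** This also stands. Strength, power, SF-36 and PROMIS are collected too and are not limited by the SPPB maximum. They measure muscle performance or self-report, however, and do not replace observed gait and chair rise.
- **The size is assumed throughout.** True. The direction follows from the bound; the amount does not.
- **The timed tasks are not shown to be more powerful.** Step 6 bears this out. A reader might infer that the summary should be demoted to a descriptive measure and replaced by the two times. The documents do not support that. They do not show that either task alone would do better at a low or moderate ceiling, and exchanging the endpoint is a debatable choice.

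**Conclusion.** The point holds as a limited one. The stated SPPB score has a ceiling that entrants may already have reached, and all participants train, so the arm difference in the summary at Week 16 is biased toward zero. If 10% to 40% enter at 12, the illustration puts the observed effect at about 0.68 to 0.40 points instead of 0.80, and power at about 71% to 54% instead of 77%. The share at 12, SD, correlation, training gain and drug effect are all assumptions.

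A reader might infer that the trial's main comparisons are compromised, or that power on function is as low as 31%. Neither is supported. The Aim 1 outcomes do not depend on the SPPB maximum, and the lowest figures require a nearly empty 3-8 stratum. What is supported is that a null SPPB summary, taken alone, should not be read as absence of functional benefit.

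**What to change.** In the Study Design section (Week 16 assessments) and the SPPB paragraph of Research Procedures:

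- Keep the 0-12 summary as it is used now.
- Add 4-meter gait speed and five-repetition chair-stand time at Week 16 as continuous functional outcomes, each adjusted for its own pre-treatment value. State how the two gait trials are combined.
- Report the proportion scoring 12 by arm and visit, and say that a null summary will be interpreted together with these results.

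No new visit or procedure is needed, because both tasks are already performed and timed. The cost is a few sentences, two more outcomes that must be labelled secondary or brought under multiplicity control, and a rule for participants who cannot complete the chair stand. The balance times are left out because nothing in the documents shows that they are free of a ceiling. If the analysis section or Table 1 already specifies these measures, a citation to it is enough.
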